8.3 Analysis Methods

The ITT population will be used in all analyses unless otherwise stated. The alpha level for determining significance will be set to 0.05 for all inference tests. The mixed models analyses described below automatically adjust for missing values; there will be no further imputation or adjustments for missing values. During the analysis of the primary hypothesis, treatment allocation will be masked (i.e., groups will be labeled A and B) during the statistical programming and unmasked only after the statistical programming code has been finalized.

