## 11.3 Analysis Samples

### 11.3.1 Intention-To-Treat Sample

Consistent with the primary statistical method that will use a linear mixed model (also called "mixed model repeated measures" model), the intention-to-treat sample is defined as all study participants who have at least one valid measurement of the primary endpoint at Visit 2 or later. A "valid" assessment for the primary endpoint is defined as at least 4 daily reports of pain intensity and duration collected in the 7-day period prior to the visit (Section 2.5.1). Treatment group allocation will be defined as the study arm into which the subject was randomized regardless of the actual study treatment received. By necessity, the intention-to-treat sample excludes participants who provide no data for the primary endpoint after randomization. Note that follow-up assessments will be included in the intention-to-treat analysis when sufficient diary data are collected at the follow-up assessment, even if there were protocol violations. Likewise, the intention-to-treat sample will include all available follow-up assessments from any discontinued participants.

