4. ANALYSIS POPULATIONS

4.1 Intention-to-Treat Population

Section 11.3.1 of the protocol defines the intention-to-treat (ITT) sample as follows:

Consistent with the primary statistical method that will use a linear mixed model, the intention-to-treat (ITT) sample is defined as all study participants who have at least one valid measurement of the primary endpoint (at Visit 2 or later. A "valid" assessment for the primary endpoint is defined as at least 4 daily reports of pain intensity and duration collected in the 7-day period prior to the visit (Section 2.5.1 of the protocol). Treatment group allocation will be defined as the study arm into which the subject was randomized regardless of the actual study treatment received. By necessity, the ITT sample excludes participants who provide no data for the primary endpoint after randomization. Note that follow-up

Version 3.0 Page 8 of 25

assessments will be included in the ITT analysis when sufficient diary data are collected at the follow-up assessment, even if there were protocol violations. Likewise, the ITT sample will include all available follow-up assessments from any discontinued participants.

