As secondary efficacy analyses, the above primary hypothesis analyses will be repeated on the PP population. The results of the ITT and PP population based analyses will be reported separately. If it appears reasonable to assume that the results of the primary hypothesis are independent of choice of the analysis population (ITT or PP), then all subsequent analyses will be performed on the ITT population only. Stratified analysis will estimate ITT treatment effects separately for the two sexes and for the main racial-ethnic groups. The analysis will be descriptive, reporting means and 95% confidence intervals. There will be no hypothesis tests of efficacy within demographic subgroups because of the expected small numbers of males and minorities.

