8.3.2 Secondary Efficacy Analyses

For secondary efficacy measures that are continuous variables or counts (Table 8-1), the effect of treatment arm on the net change in the secondary efficacy measures will be analyzed using the same statistical model as in the primary efficacy analyses but with derived scores for each measure used as the dependent variables. In summary, data from all applicable visits will be analyzed with linear mixed models as described for the primary hypothesis. For most secondary efficacy measures, the data were collected at V1, V3 and V4, although the schedule differed for a few data forms as shown in Appendix A. Outcomes will be reported at each study visit using number of subjects, the mean \pm standard error, and 95% confidence limits of the mean, median, min, and max. Tests for significance of treatment group differences in the change from V1 to V4 will be evaluated with linear mixed models as described for the primary hypothesis. P-value testing for the main effects of treatment allocation will be reported for overall treatment effect and for the treatment effects at each study visit.

For secondary efficacy variables measured on an ordinal scale, the non-parametric signed-rank Wilcoxon test will instead be used to test for change between visits within each treatment group,

Version 3.0 Page 15 of 25

and there will be no adjustment for covariates. Patients' Global Impression of Change is the one secondary-efficacy measure that was not measured at V0 or V1, so the test for treatment group differences in that outcome will be evaluated using the Wilcoxon rank sum.

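### The diary-based intention-to-treat set also governs secondary efficacy outcomes that do not use the diary, so some measured data would be dropped without need

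*SAP*

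**What the plan says.** SAP 4.1 repeats the definition in Protocol 11.3.1. The intention-to-treat (ITT) set is "all study participants who have at least one valid measurement of the primary endpoint (at Visit 2 or later", and a valid assessment is "defined as at least 4 daily reports of pain intensity and duration collected in the 7-day period prior to the visit". The protocol gives its reason: "By necessity, the intention-to-treat sample excludes participants who provide no data for the primary endpoint after randomization".

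SAP 8.3 then sets the default: "The ITT population will be used in all analyses unless otherwise stated". SAP 8.3.1 adds that if the ITT and per-protocol (PP) results appear to agree, "then all subsequent analyses will be performed on the ITT population only". For secondary measures that are continuous or counts, SAP 8.3.2 says that "data from all applicable visits will be analyzed with linear mixed models as described for the primary hypothesis". It gives no separate population for these or for the ordinal outcomes. For medication use it makes one outcome-specific exclusion: about 20 early participants at one site, whose type of pain was not recorded, are left out of the rescue-medication model and kept in the over-the-counter model.

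SAP 9.1 assigns all safety analyses to the Safety population, which has no diary condition.

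**The concern.** The reason given for the exclusion is that a participant without a diary endpoint has nothing to analyse. That is true of the pain index and of diary pain intensity and duration. It is not true of the patient global impression of change (PGIC), GCPS, JFLS, HADS, PSQI, PSS, SCL-90R, SF-12, HIT-6, heat and pressure pain tests, TMD examination, SF-McGill, or days on rescue or over-the-counter medication. All of these are collected by questionnaire, examination or medication record at visits.

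For those outcomes the rule is a post-randomization exclusion based on compliance with a different instrument. It discards observed data from named secondary hypotheses and weakens the ITT label. If diary failure differed between arms, the comparison would no longer be fully protected by randomization.

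**Working it through.** **Step 1. Can such participants exist under the protocol's rules?**
- Protocol 7.1.10 treats diary noncompliance at Visits 2 to 5 as a protocol deviation. Protocol 4.4.4 does not list it as a reason for withdrawal, so clinic visits and questionnaires can continue.
- Protocol 6.5 allows an Early Termination Visit with every Visit 4 procedure. Someone who stops within days of the first dose could supply those outcomes with fewer than 4 diary days since randomization.

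**Step 2. Does another rule bring them back?**
- The PP set (SAP 4.2) is a subset of ITT, so it does not.
- SAP 8.1 relies on the mixed model to accommodate missing values. These participants are removed before the model is fitted, so their observed values never enter it.
- The covariates are not an obstacle. The medication models adjust for the Visit 1 pain index, and Protocol 4.1 and 6.3.1 require at least 4 diary entries in the week before Visit 1.

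**Step 3. How many?** The documents give neither a rate of invalid weeks nor a within-person correlation. The 10% loss to follow-up in Protocol 11.2 is a different quantity. Both inputs are therefore assumed, and all 200 participants are taken to attend every counted visit.

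Let p be the proportion of invalid visit weeks, ρ the within-person correlation, and k the number of visits that can qualify a participant. With s = (1 − ρ)/ρ and a = p·s, the beta-binomial gives

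P(all k invalid) = product over j = 0, …, k − 1 of (a + j)/(s + j), which is p^k when ρ = 0.

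Worked case, p = 0.10:
- ρ = 0.2: s = 4, a = 0.4. For k = 3, (0.4/4)(1.4/5)(2.4/6) = 0.0112, and × 200 = 2.2. For k = 4, 0.0112 × 3.4/7 = 0.00544, and × 200 = 1.1.
- ρ = 0.5: s = 1, a = 0.1. For k = 3, (0.1)(1.1/2)(2.1/3) = 0.0385, and × 200 = 7.7. For k = 4, 0.0385 × 3.1/4 = 0.0298, and × 200 = 6.0.

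Expected number excluded, of 200, at ρ = 0 / 0.2 / 0.5:

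| Assumed p | Visits 2–4 (k = 3) | Visits 2–5 (k = 4) |
|---|---|---|
| 0.05 | 0.03 / 0.9 / 3.6 | 0.001 / 0.4 / 2.7 |
| 0.10 | 0.2 / 2.2 / 7.7 | 0.02 / 1.1 / 6.0 |
| 0.20 | 1.6 / 6.7 / 17.6 | 0.3 / 3.7 / 14.1 |

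Both columns are needed because the text is not settled. Read literally, a valid week at Visit 2 or later includes Visit 5, where diaries are still collected. Protocol 2.5.1 computes the index after randomization for treatment-phase weeks only, and SAP Table 8-1 computes net change at Visits 2 to 4. Those passages favour the three-visit reading.

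**Step 4. What does it cost in power?** Take an illustrative secondary outcome with 80% power at 100 per arm (two-sided 0.05). Its standardized difference is (1.960 + 0.842) × √(2/100) = 0.396. With n per arm, power = Φ(0.396/√(2/n) − 1.960):

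| Excluded | Analysed | Power |
|---|---|---|
| 1% | 198 | 79.6% |
| 2% | 196 | 79.2% |
| 5% | 190 | 78.0% |
| 10% | 180 | 75.7% |

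**The case against.** The best defence has four parts.

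- **The group is small.** Everyone randomized has just met the same 4-of-7 diary standard, and one valid later week is enough to enter ITT. This stands. It also means that the upper corner of the table, which pairs the highest assumed rate with the highest assumed correlation, deserves little weight.
- **Many people who fail the rule have nothing to lose.** Most of these outcomes are first measured after baseline at Visit 3. Participants lost before then without an Early Termination Visit have no such data to discard. This also stands.
- **A single set keeps a common denominator, and the remedy is itself a data-availability condition.** Both are true, and the remedy is not a full ITT analysis. But it conditions on the outcome being analysed, whereas the present rule conditions on a different one.
- **Bias is conjectural.** Protocol 8.1 lists fatigue, sleep problems and depression as expected drug effects, and the diary is completed at the end of each day, so a difference between arms is plausible. Nothing in the documents links those effects to diary completion.

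A reader might infer that the rule reaches every analysis, including adverse events, or that it distorts the primary result. The documents do not support either. Safety uses its own population, and the primary and COMT-interaction analyses use the pain index, for which the necessity argument is sound. Vital signs appear among the efficacy variables in SAP Table 8-1 and are caught there, but their safety tabulation under SAP 9.4 is not.

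**Conclusion.** The point holds for secondary efficacy outcomes that do not come from the diary. By the stated rules, a randomized participant with no valid diary week at Visit 2 or later is dropped from those analyses even when the outcomes were measured, and the protocol's reason does not cover the exclusion.

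The effect is probably small. At an assumed 10% of invalid weeks it is about 0 to 8 of 200 on the Visit 2–4 reading and about 0 to 6 if Visit 5 counts. These counts rest on an assumed rate, an assumed correlation of 0 to 0.5, and full attendance. They do not model early terminations. Eight of 200 is 4%, so the power loss would lie between the 2% and 5% rows above. The main issue is an avoidable exclusion under an ITT label. It would be too strong to read this as evidence of bias: selection by arm is possible, not shown. This is an inexpensive improvement, not a threat to the trial's main conclusion.

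**What to change.** In SAP 4.1 and 8.3:
- Keep the present set for the pain index and for diary intensity and duration.
- Analyse each other secondary efficacy outcome in all randomized participants, as randomized, with at least one post-baseline value of that outcome.
- For the medication models, include all randomized participants with medication data after Visit 1, and keep the existing exclusion of about 20 participants from the rescue-medication model.
- Report by arm how many participants the diary rule would have excluded from each of these analyses, so that a reader can judge whether it mattered.

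The cost is a short SAP amendment and a population flag per outcome. Denominators will differ slightly between outcomes. The SAP is already set up for this: section 3 reports the number with non-missing values for each continuous variable, and section 8.3.2 already tailors a set to one outcome.

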8.3.1 Primary Efficacy Analyses

The primary statistical analysis to evaluate the primary hypothesis will use all data from the ITT analytical sample in a linear mixed model. Mixed models will be used to analyze the treatment effect at V4 (Proc Mixed, SAS, version 9.4 or greater, SAS Institute, Inc., Cary, North Carolina). The mixed model will include the net change in the mean pain index as the dependent variable. The model's independent variables will include fixed effects for site, sex, race-ethnicity, the

Version 3.0 Page 14 of 25

mean pain index at V1 (as a baseline covariate), visit (V2, V3 and V4), treatment allocation (active versus placebo), and a visit by treatment interaction. Participants will be included as a random effect in the mixed model. The mixed model will be run twice assuming either a compound symmetry or an unstructured variance structure. The mixed model achieving the lowest Akaike information criterion will be selected as the best model and used for reporting of results. The model's denominator degrees of freedom will be adjusted for any possible effects of sample imbalances due to any missing values using Kenward Roger's method in SAS. For descriptive purposes (and regardless of the P-value for efficacy at Visit 4), efficacy estimates at each visit (2, 3 and 4) will be described in terms of adjusted means and 95% confidence intervals.

If there is a treatment effect, then "responder analyses" will be performed to compare the responder status of the treatment allocation groups. Participants will have their binomial responder status classified at both the 30% and 50% response threshold levels. The odds ratios of treatment group allocation on the responder status of participants at both the 30% and 50% threshold levels will be estimated using logistic regression with covariate adjustments for site and V1 weekly mean pain index. The odds ratio for the effect of treatment allocation on responder status for both the 30% and 50% threshold levels will be reported with their 95% confidence limits and their associated P-values.

As secondary efficacy analyses, the above primary hypothesis analyses will be repeated on the PP population. The results of the ITT and PP population based analyses will be reported separately. If it appears reasonable to assume that the results of the primary hypothesis are independent of choice of the analysis population (ITT or PP), then all subsequent analyses will be performed on the ITT population only. Stratified analysis will estimate ITT treatment effects separately for the two sexes and for the main racial-ethnic groups. The analysis will be descriptive, reporting means and 95% confidence intervals. There will be no hypothesis tests of efficacy within demographic subgroups because of the expected small numbers of males and minorities.

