### 3 STUDY DESIGN OVERVIEW

Two hundred participants with chronic TMD recruited at 3 clinical sites, will be randomized in a 1:1 ratio to propranolol or placebo in a parallel-group, blinded clinical trial. Participants will be limited to age 18 – 65 years because pharmacokinetic data are not available for patients over 65 years for extended-release propranolol hydrochloride; standard propranolol drug clearance is decreased and half-life increased in older populations. Additionally, with aging, arthralgia, osteoarthritis, and osteoarthritis become more prevalent TMD diagnoses than myalgia; propranolol will not be effective for these types of TMD.

Participants will attend 6 clinic visits over a period of 12 to 15 weeks (Figure 1). The study should be completed in 3 years, with participant recruitment occurring during years 1 and 2.

Prescreening will be performed either in the clinic or over the telephone, and potentially eligible participants will be scheduled for a Screening and Baseline Visit (Visit 0). During Visit 0, participants will be consented and evaluated for eligibility, and information including demographics, medical history, and concomitant medications will be collected. Additionally, participants will be assessed for pain, health status, jaw function, emotional functioning, sleep, and somatic symptoms, among other measures. Procedures will include clinical examinations and tests and the dispensation of various questionnaires, all of which are listed in the Schedule of Events (Appendix A).

At Visit 1, participants who show compliance with the Daily Symptom Diary (at least 4 daily entries within 7 days) and meet the pain score and all other eligibility requirements will be randomized to propranolol or placebo and will begin a 10-week drug treatment phase that is divided into 1 week of drug titration, 8 weeks of drug maintenance, and 1 week of drug tapering. During that period, Visits 2-4 will take place, and many of the baseline assessments will be repeated. The final study visit, Visit 5, will occur 1 week after drug tapering ends and 2 weeks after Visit 4.

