## 11.2 Sample Size Considerations

This study plans to randomize 200 participants, which will provide 94% power (alpha = 0.05) to detect a difference between a 27% reduction in pain index in the propranolol arm and a 9% reduction in the placebo arm (primary hypothesis). Assuming haplotype distributions and within-haplotype treatment effects that are similar to those observed in the pilot study, the same sample size would provide 61% power (alpha = 0.05) to detect an interaction between haplotype and treatment group (secondary hypothesis). The assumptions for these power calculations are shown in the following table. Power calculations were made using the GLMPOWER procedure in SAS, which assumes a data structure of one observation per person. This is a simplification of the situation that will occur with the linear mixed model described in Section 11.4.1 in which efficacy will be evaluated using a data structure in which most participants will have three observations per person. The simplified power calculations are shown here because conventional software for power calculations does not deal with the more complex situation of linear mixed models.

		Primary Hypothesis		Secondary Hypothesis					
COMT haplotype		All haplotypes		0 LPS copies		1 LPS copy		2 LPS copies	
Treatment arm		Drug	Placebo	Drug	Placebo	Drug	Placebo	Drug	Placebo
% of participants (N = 200)		50%	50%	15%	15%	25%	25%	10%	10%
Mean baseline pain index		3000	3000	3000	3000	3000	3000	3000	3000
Net change		-810	-270	-1350	-270	-810	-270	-270	-270
Percentage change		-27	-9	-45	-9	-27	-9	-9	-9

\* LPS stands for low pain sensitive, one of the major haplotypes of *COMT*. The standard deviation for the mean baseline pain index is estimated to be 1190. The net change takes into account a 10% lost-to-follow-up rate and imputation using the last observation carried forward approach.

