### 11.4.1 Analysis of the Primary Hypothesis

The primary statistical analysis to evaluate the primary hypothesis will use all data from the intention-to-treat analytical sample in a linear mixed model. During the analysis of the primary hypothesis, treatment allocation will be masked (i.e., groups will be labeled A and B). Treatment allocation will be unmasked for further analyses.

---

The dependent variable will be the participant's change in the weekly pain index, computed as the weekly pain index at the follow-up visit (i.e., at Visit 2, Visit 3, or Visit 4) minus the Visit 1 weekly pain index. Explanatory variables will comprise fixed factors and a continuous covariate. The fixed factors will include the following: (a) treatment allocation (two categories) (b) visit sequence (three categories); (c) interaction of treatment allocation and visit sequence (two dummy variables); and (d) covariates of study site (three categories), sex (two categories) and race/ethnicity (probably three categories: non-Hispanic White, non-Hispanic Black, and other/multiple racial or ethnic groups – the final number of conditions will be dictated by the frequency distribution of race/ethnicity in the study sample). The baseline score collected at Visit 1 will be the continuous covariate, modeled as a fixed effect. The study participant will be modeled as a random factor.

In a linear mixed model containing all predictor variables including the interaction terms for visit and treatment allocation, the primary treatment effect will be tested at Visit 4. The null hypothesis of no treatment effect will be rejected if the P-value at Visit 4 is  $\leq 0.05$ . For descriptive purposes (and regardless of the P-value for efficacy at Visit 4), efficacy estimates at each visit (2, 3 and 4) will be described in terms of adjusted means and 95% confidence intervals.

If the propranolol treatment arm has a greater reduction in the weekly pain index than the placebo arm at Visit 4, a threshold of "responder analysis" will be undertaken to estimate the odds of at least a 30% reduction, relative to Visit 1, in the pain index at Visit 4. Likewise, another threshold of responder analysis will describe the odds of experiencing at least a 50% reduction. These estimates will be calculated from a logistic model in which the dependent variable is a binary variable that dichotomizes the change score at the appropriate threshold (i.e.,  $\geq 30\%$  or  $\geq 50\%$ ).

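### The primary model applies one baseline slope at weeks 1, 5 and 9. Letting it vary by visit would protect the precision of the Visit 4 test at almost no cost.

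*SAP*

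**What the plan says.** SAP 8.3.1 models the change in weekly mean pain index from V1 at V2, V3 and V4. Besides site, sex and race-ethnicity, its fixed effects are "mean pain index at V1 (as a baseline covariate), visit (V2, V3 and V4), treatment allocation (active versus placebo"), plus a visit-by-treatment interaction. The model is fitted with compound symmetry and with unstructured covariance, and the fit with the lower AIC is reported.

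Protocol 11.4.1 gives the same terms and says of the covariate: "The baseline score collected at Visit 1 will be the continuous covariate, modeled as a fixed effect". It places the primary test at Visit 4. Neither document lists a baseline-by-visit term or explains why the slope should be the same at every visit.

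The model is reused. SAP 8.3.1 repeats it in the per-protocol population. SAP 8.3.2 applies it to continuous and count secondary measures and extends it for the COMT interaction. SAP Section 11 records no changes from the protocol's analyses.

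**The concern.** The plan lets the treatment effect differ by visit and allows unstructured covariance, but holds the baseline effect constant. V2 is one week after baseline, at the end of titration. V4 is nine weeks after baseline, following eight weeks of maintenance. Weekly diary means one week apart would usually agree more closely than means nine weeks apart, so the right slope at V4 probably differs from the right slope at V2.

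Under unstructured covariance the common slope is weighted towards the visit with the least residual variance. When the baseline correlation decays and the SDs are similar, that visit is V2. The decision rests on V4, so what is at stake is the precision of the decisive estimate: part of any chance baseline difference between the arms stays in it.

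**Working it through.** **Inputs from the documents**
- Size: "This study plans to randomize 200 participants, which will provide 94% power (alpha = 0.05"); participants "will be randomized in a 1:1 ratio to propranolol or placebo in a parallel-group, blinded clinical trial", so n = 100 per arm.
- Effect: "a 27% reduction in pain index in the propranolol arm and a 9% reduction in the placebo arm", from a baseline of 3000. The net changes are -810 and -270, a difference of 540.
- Spread: "The standard deviation for the mean baseline pain index is estimated to be 1190". No SD of change and no V4 SD is given.
- Level: "The alpha level for determining significance will be set to 0.05 for all inference tests". Sidedness is not stated; two-sided is used below.
- Dropout: "The net change takes into account a 10% lost-to-follow-up rate and imputation using the last observation carried forward approach". It is already inside the net change, so n is not reduced again.

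**Inputs assumed, because the documents do not give them**
- Baseline correlations r2/r3/r4 at V2/V3/V4, as in the table.
- Follow-up correlations (V2-V3/V2-V4/V3-V4) of .6/.5/.6, .7/.6/.7 and .8/.7/.8. They set the width of each range.
- SD 1190 at every visit, complete data, and no allowance for site, sex or race-ethnicity.

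**The plan's own power figure.** The SE with no baseline gain is 1190 × √(2/100) = 168.3. Then 540/168.3 = 3.209, and two-sided power is Φ(3.209 - 1.960) = 89.4%. The stated 94% appears with one-sided 0.05, Φ(3.209 - 1.645) = 94.1%, or with the haplotype-weighted difference 0.3×1080 + 0.5×540 + 0.2×0 = 594, which gives 94.2% two-sided. This calculation uses one observation per person, so it neither supports nor contradicts the point here.

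**Formulas.** Work in units of 1190².
1. The slope for change at visit k is b_k = r_k - 1.
2. The residual covariance is R = C - rr', where C holds the follow-up correlations. At V4, R44 = 1 - r4².
3. Under unstructured covariance the common slope is b_c = (1'Σ⁻¹b)/(1'Σ⁻¹1), with Σ = R + (b - b_c)(b - b_c)', solved by iteration. Under compound symmetry b_c is the simple mean of the b_k.
4. The V4 variance is (2/n) × 1190² × R44 with visit-specific slopes. With a common slope it is larger by the factor 1 + (b4 - b_c)²/R44.

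**One row in full.** Take .80/.65/.50 with follow-up correlations .7/.6/.7.
- b4 = -0.500 and b_c = -0.268. Excess variance is 0.2324²/0.75 = 7.2%.
- SE with visit-specific slopes: 1190 × √(0.02 × 0.75) = 145.7. SE as planned: 145.7 × √1.072 = 150.9.
- Power: Φ(540/145.7 - 1.960) = 96.0%, against Φ(540/150.9 - 1.960) = 94.7%.
- A one-SE baseline imbalance (168.3) leaves 168.3 × 0.2324 = 39 units in the V4 estimate. (39.1/145.7)² = 7.2%, so the residual imbalance and the lost precision are the same quantity.

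**All rows**

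| r2/r3/r4 | Excess variance, unstructured | Excess, compound symmetry | Power as planned | Power with the term |
|---|---|---|---|---|
| .60/.60/.60 | 0% | 0% | 98.0% | 98.0% |
| .70/.65/.60 | 0.5-0.6% | 0.4% | 97.9% | 98.0% |
| .70/.60/.50 | 2.1-2.7% | 1.3% | 95.5-95.6% | 96.0% |
| .80/.65/.50 | 6.1-9.3% | 3.0% | 94.3-94.9% | 96.0% |
| .80/.60/.40 | 11.8-20.8% | 4.8% | 89.0-91.2% | 93.8% |

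The power columns use unstructured covariance.

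**Sensitivity to SD.** For .80/.65/.50 with .7/.6/.7, the 7.2% becomes 2.8% if the SDs at V2/V3/V4 are 1, 1.1 and 1.2 times 1190. It becomes 13.2% if they are 1, 0.9 and 0.8 times.

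**Simulation.** 1500 trials per scenario were run, with 200 participants, complete data and the planned AIC choice. The baseline correlations were .6/.6/.6, .7/.6/.55, .8/.6/.5 and .85/.55/.4. The common-slope V4 estimate was unbiased, and type I error under the selected model was 4.4% to 5.5%. AIC chose unstructured covariance in over 99% of trials in the scenarios with decay.

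**The case against.** The strongest reply is that this is a refinement and not an error. Protocol and SAP agree on the model, it adjusts for baseline, and it tests treatment at V4. In every assumed row except the last, the planned model's SE stays below the unadjusted 168.3; in the last row it runs from 163.1 to 169.5. The correlations are assumptions, and with equal slopes nothing is lost. All of that stands, and it limits the point to efficiency.

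Stronger readings that a reader might infer are not supported:
- *The imbalance is left uncorrected.* The V1 index is a covariate and the outcome is change from V1. In the worked row the common slope is -0.268 where -0.500 is needed, so about half of the required adjustment is made.
- *The primary test is biased or invalid.* Randomisation keeps the estimate unbiased, and simulated type I error was held under the planned selection rule.
- *There are two harms, lost precision and shifted estimates.* The arithmetic shows one effect.
- *A loss above 10% is to be expected.* Among the rows with equal SDs, only .80/.60/.40 exceeds it.
- *Missing V4 values are materially affected.* The slope does enter the model for those participants, but the calculations use complete data, so no size can be claimed.

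**Conclusion.** The omission is a fact of both documents; its cost is conditional. If the baseline correlation decays, the V4 estimate is somewhat less precise than the same data allow. The excess variance runs from 0% with equal slopes, through about 0.5% to 3% for mild decay and 6% to 9% for .80/.65/.50, to 12% to 21% for .80/.60/.40. For a difference of 540 that is about 0 to 5 points of power.

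These figures rest on SD 1190 at all visits, complete data, unstructured covariance and follow-up correlations of about .5 to .8. They are illustrations, not bounds: steeper decay or falling SDs would raise them, and rising SDs would lower them. The excess is smaller under compound symmetry, but AIC is unlikely to select that structure when the correlation decays. The point concerns efficiency and the accuracy of the estimate given the imbalance that actually occurs; the validity of the trial is not in question. It is a free improvement.

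**What to change.** Add a V1 mean pain index by visit interaction to the primary model in SAP 8.3.1. Do this before the statistical code is finalised, since SAP 8.3 keeps allocation masked until then.

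Carry the term into the per-protocol analysis, the linear mixed models for secondary measures and the COMT interaction model. Where a secondary model uses that outcome's own baseline as the covariate, interact that baseline with visit instead. Protocol 11.4.1 fixes the present model, so list the addition as a change in SAP Section 11.

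The cost is two fixed-effect parameters with three follow-up visits, or one with two, and no new data. If the slopes turn out equal the loss is negligible: in the equal-slope simulation with a difference of 540, the mean model SE under unstructured covariance was 134.4 with the term and 134.1 without it.
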